Screening/Eligibility: During screening, eligibility will be determined using scripted questions: Inclusion/Exclusion Criteria. Potential subjects will be invited to participate in the study, demographics will be recorded. **Inclusion Criteria:** Postmenopausal women with clinically diagnosed vulvovaginal atrophy, age ≥ 55 years old and a screening vaginal pH of ≥ 5 , without menses for ≥ 12 months, no uterovaginal or vaginal vault prolapse beyond the hymen. **Exclusionary Criteria:** 1) Patients with BMI $\geq 35\text{kg}/\text{m}^2$. 2) Any patients with infections requiring antibiotic or antifungal therapy during the study period or within the last month or during the study period. 3) Study patients may not use any vaginal suppositories, douches, or vaginal hygiene wipes within the month preceding enrollment. 4) Patients receiving ongoing hormone replacement therapy. Patients already on hormone therapy, will be allowed to undergo a "wash out" period of estrogen or progesterone products for one month prior to enrollment. 5) Patients requiring concurrent use of steroid creams for other indications (e.g. lichen sclerosis). 6) Additional exclusions included patients with systemic conditions requiring immunosuppressive drugs, currently receiving chemotherapy, or history of pelvic radiation. 7) Any patients with contraindications to vaginal estrogen therapy including vaginal bleeding of unknown etiology. 8) Any patients with history of connective tissue disease. 9) Current tobacco use.

D.2. Study Design

The intention of this study is for each of the subjects to serve as her own control. Twenty patients will receive the treatment intervention. Five will not receive the treatment intervention. The five subjects not receiving

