treatment are intended to serve as a control cohort to demonstrate stability of the microbiome over the study period. It is anticipated that unlike premenopausal subjects, the postmenopausal subjects not undergoing treatment (control group) will have little variation of the microbiome over the eight weeks. Each of the twenty-five subjects will be sampled for microbiome and inflammatory biomarker analysis at three different locations (vagina, bladder, rectum) at two separate time points (Baseline Visit 1 and after eight weeks of vaginal estrogen therapy, Visit 2). This will yield a total of 300 samples for the study. The treated subjects (20) and untreated (5) subjects may be compared to each other but that is not the primary aim of this study.

Intervention: 1g conjugated estrogen (CE) cream given nightly for 2 weeks then twice-weekly to complete planned eight weeks therapy. This specific dose and frequency has been shown to improve objective and subjective measures of vaginal epithelium in previous studies (23, 27). It has also been shown to achieve objective improvements in as little as three to four weeks (23). Additionally, this dose and regimen is already commonly used and will provide excellent external generalizability.

D.3. Specific Aims

D.3.1. Specific Aim – 1: To assess the quantitative change in relative abundance of Lactobacillus among the community composition of bacteria in the vagina pre- and post- vaginal estrogen therapy. **Hypothesis:** A statistically significant quantitative increase in the relative abundance of Lactobacillus will be seen.

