Microbiome Analysis Statement of Rigor: Several quality controls are performed: 1) removing sequences with low quality scores, those matching human databases and low-duplicates and 2) merging paired reads and discarding sequences with substantial differences. Results from the UAB Microbiome Resource pipeline showed that duplicate samples had significant co-clustering on Principal Coordinate Analysis (PCoA) plots. Using 16S rRNA gene and whole genome DNA sequences from 20 known species, we are able to correctly identify organisms with unique 16S rRNA V4 genes to the genus and even species level and predict genetic pathways. **Sample Size and Power Rationale:** Our sample size calculation is based upon our primary aim to evaluate the expected quantitative change in relative abundance of Lactobacillus genus and spp among the community composition of bacteria in the vagina. There's an abundance of research reporting the normalization of the vagina by objective measures by various routes of estrogen therapy, specifically by serving to facilitate the increase of the relative Lactobacillus presence. However, it is difficult to define how much of an increase in Lactobacillus is needed to be clinically relevant. As previously stated there is no previous study by which to reference in predicting what the expected change in Lactobacillus may be in the setting of vaginal estrogen therapy. A previous study (22) has compared a cohort of atrophic vaginitis (AV) patients who received low dose oral estrogen therapy to a healthy control (not receiving therapy); all patients were postmenopausal meeting strict criteria. Vaginal sampling took place at baseline, two weeks,

Table 1. Description of Sample Numbers and Locations.

SAMPLE LOCATION	Pre-Treatment	Post-Treatment
VAGINA		
Inflammatory Biomarkers	25	25
Microbiome	25	25
BLADDER		
Inflammatory Biomarkers	25	25
Microbiome	25	25
RECTUM		
Inflammatory Biomarkers	25	25
Microbiome	25	25

and at four weeks after treatment initiation. Among the AV group the relative abundance of Lactobacillus pretreatment was 0.112 ± 0.164 . At 4 weeks of oral estrogen therapy the Lactobacillus abundance rose dramatically to 0.71 ± 0.375 . The baseline abundance among the “healthy” untreated postmenopausal cohort was 0.532 ± 0.403 and virtually without change over the four week period.

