Based on these results, we expect the relative abundance of Lactobacillus in our cohort to be somewhere between 0.112-0.532 at baseline. As the selection criteria of our cohort does not include VVA symptomatology, we expect the relative abundance of Lactobacillus spp to be approximately 0.4 ± 0.3 . **With a Type-1 error of 0.05, we estimate with 80% power that we can detect an effect size of 0.2 increase (0.4→0.6) in the relative abundance of Lactobacillus spp with a treatment sample size of 20 patients.**

Biostatistical Analysis Plan: The following microbial community-level analyses will be performed to investigate the overall microbiome differences between the pre-treatment and post-treatments groups using the R package **phyloseq** (Table 2)(32).

Table 2. Overview of Community-Level Microbiome Analysis

Outcome	Measurements	Two-group comparisons
Alpha diversity (diversity within a sample)	Shannon, Chao, Simpson indices	t-tests, Mann-Whitney U
Beta diversity (diversity between samples, overall microbiota composition)	Bray-Curtis, unweighted UniFrac, weighted UniFrac (represented by PCoA to visualize clustering)	PERMANOVA or Dirichlet-multinomial distribution with Wald-type test

To identify individual taxa significantly associated with vaginal estrogen treatment, taxa-specific analyses will be performed. Given the distinct properties of microbiome data (compositional counts/proportions, varying total sequence reads across samples, over-dispersion), microbiome counts, transformations of microbiome counts, and beta regression for relative abundance will be used (33-39). To deal with zero-inflation of microbiome data, we will employ zero-inflated models: negative binomial (for count data), Gaussian (for logarithm or arcsine square root transformations), beta regression (for relative abundance) – which allow analysis of multiple covariates which may vary between treatment and non-treatment groups (38, 40-43). An R package *bmzim* for these models will be used. Standard procedures (e.g. Holm's, Hochberg's, Hommel's, Benjamini and Hochberg's methods) will be used to calculate p-values adjusted for multiple comparisons.

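### The 20 treated women are sized for Lactobacillus at 5% and 80%, but the Aim 1 analysis plan names no Lactobacillus test and adjusts its only individual-taxon analysis for multiplicity, so the 80% is not secured as written

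*Combined protocol and SAP*

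**What the plan says.** All references are to the combined protocol and SAP.

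- **Aim.** The Aim 1 hypothesis in D.3.1 is a formal one: "A statistically significant quantitative increase in the relative abundance of Lactobacillus will be seen".
- **Sizing.** The Sample Size and Power Rationale in D.3.1 states: "Our sample size calculation is based upon our primary aim to evaluate the expected quantitative change in relative abundance of Lactobacillus genus and spp". It gives the expected level ("we expect the relative abundance of Lactobacillus spp to be approximately 0.4 ± 0.3") and then the claim: "With a Type-1 error of 0.05, we estimate with 80% power that we can detect an effect size of 0.2 increase", from 0.4 to 0.6, with 20 treated women. It names no test, does not say whether the test is one- or two-sided, and makes no allowance for multiplicity.
- **Design.** D.2 makes the comparison within-woman: "The intention of this study is for each of the subjects to serve as her own control".
- **Analysis.** The Biostatistical Analysis Plan in D.3.1 has two parts. Table 2 covers alpha and beta diversity. The second part is a screen: "To identify individual taxa significantly associated with vaginal estrogen treatment, taxa-specific analyses will be performed". It lists models for counts and for transformed counts, and "beta regression for relative abundance", with zero-inflated versions. None is labelled primary, and the pairing of a woman's two visits is not described. The paragraph ends with Holm, Hochberg, Hommel and Benjamini-Hochberg as examples of procedures that "will be used to calculate p-values adjusted for multiple comparisons".
- **Elsewhere.** The Aim 2 plan in D.3.2 relates taxa to cytokines, maturation index and pH. It adds no pre/post test of Lactobacillus.

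**The concern.** The hypothesis that determined the sample size has no written test of its own. The analysis plan does not mention Lactobacillus, so the only written route to a Lactobacillus p-value is the taxa screen. There, whether a rise of 0.2 is declared significant can depend on three things the plan leaves open: how many other taxa enter the family, which listed procedure is used (the examples mix family-wise and false-discovery methods), and whether the chosen model respects the pairing. The power statement describes a different situation, namely one test at 0.05. Leaving the model, taxonomic level and adjustment open also allows them to be chosen after the data are seen.

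**Working it through.** **Inputs from the documents.** Change δ = 0.6 − 0.4 = 0.2; n = 20 treated women; α = 0.05; claimed power 80%; an SD of 0.3, attached to the expected abundance.

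**Inputs not in the documents, assumed here.** SD of the within-woman change (σ_d), number of taxa tested (m), sidedness, and how the other taxa move. A paired t-test stands in for the plan's models; the zero-inflated models were not simulated.

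**1. Reproduce the 80%.** For a two-sided paired t-test, the noncentrality is λ = δ√n/σ_d on n − 1 = 19 degrees of freedom. With σ_d = 0.3, λ = 0.2 × √20 / 0.3 = 2.98 and the critical value is 2.093. Power is **80.7%**, and n = 20 is the smallest n that reaches 80% (n = 19 gives 78.5%). The same test one-sided gives 89.0%. An unpaired 20 versus 20 t-test with SD 0.3 has λ = 0.2 / (0.3 × √(2/20)) = 2.11 on 38 degrees of freedom and gives 53.8%.

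**2. What the 0.3 must mean.** If the SD is 0.3 at both visits with within-woman correlation ρ, then σ_d = 0.3 × √(2(1 − ρ)).

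| ρ | σ_d | Two-sided power, no adjustment |
|---|---|---|
| 0 | 0.424 | 51.6% |
| 0.25 | 0.367 | 63.7% |
| 0.5 | 0.300 | 80.7% |
| 0.75 | 0.212 | 97.9% |

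Two-sided 80% needs ρ of about 0.49 or more. One-sided, about 0.33 is enough (65.1% at ρ = 0).

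**3. Adjustment, worst case.** Replace α by 0.05/m and keep σ_d = 0.3:

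| m | α | Power |
|---|---|---|
| 1 | 0.05 | 80.7% |
| 2 | 0.025 | 70.6% |
| 5 | 0.01 | 55.8% |
| 10 | 0.005 | 44.8% |
| 20 | 0.0025 | 34.7% |
| 50 | 0.001 | 23.6% |

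**4. Adjustment, other taxa falling as Lactobacillus rises.** Proportions sum to one, so the taxa are not independent. With two taxa, one proportion is the complement of the other and the two p-values are identical. Hochberg and Benjamini-Hochberg then compare the larger p-value with 0.05 and lose nothing, while Holm's first step is at 0.025. For more taxa, a simulation was used. Lactobacillus was beta-distributed with means 0.4 and 0.6, SD 0.3 and ρ = 0.5. The other taxa shared the remainder by Dirichlet draws, in 18 scenarios per m with 3,000 to 6,000 replicates each. Unadjusted power was 80–82%. Lactobacillus power after adjustment was:

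| m | Holm | Hochberg | Benjamini-Hochberg |
|---|---|---|---|
| 2 | 69–71% | 80–82% | 80–82% |
| 10 | 44–48% | 44–58% | 45–70% |
| 50 | 23–26% | 23–26% | 23–45% |

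**5. Pairing alone.** On the same simulated Lactobacillus data with one unadjusted test: paired t 80.5% (type I error 5.0%), signed-rank 80.1% (4.6%), unpaired t 54.0%, Mann-Whitney 54.7%.

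**6. A much larger effect.** In the oral-estrogen cohort cited in D.3.1, the change is 0.71 − 0.112 = 0.598. At zero correlation, σ_d = √(0.164² + 0.375²) = 0.409. Worst-case power is 99.9% at m = 10 and 98.8% at m = 50.

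**The case against.** The strongest reply is that the adjustment was never meant for Lactobacillus. It closes a paragraph whose stated purpose is to find taxa, whereas Lactobacillus has its own hypothesis, type I error, effect and sample just above. The 80% also matches a single unadjusted paired test. That is probably what was intended, and it limits the point: the defect is an unwritten primary test, not a declared decision to adjust it. A reader might infer that Lactobacillus will be adjusted and that the true power is 45% or less. The documents do not support that. They give neither m, nor the family, nor the procedure, and under some of the listed procedures the loss can be nil.

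Other parts of the reply also stand:

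- Sidedness is unstated and the hypothesis is directional, so the two-sided figures rest on a choice the documents do not make.
- Only the power rationale explicitly calls the Lactobacillus change the primary aim. D.1.1 describes the primary aim more broadly.
- This is a pilot, and an effect like that of the cited oral-estrogen cohort would be detected either way.

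What does not stand is the view that nothing needs changing. Aims 3 and 4 are labelled exploratory and Aim 1 is not. It carries a significance hypothesis and a power claim at 0.2, and intention does not settle the model, the pairing or the taxonomic level.

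**Conclusion.** The concern holds as a gap between the power statement and the written analysis. Followed literally, the Aim 1 plan does not secure its 80%. The loss from adjustment ranges from none (Hochberg or Benjamini-Hochberg with two taxa) to a power of about 45% (worst case, 10 taxa) or 24% (worst case, 50 taxa). An unpaired analysis without adjustment gives about 54%. These figures assume a two-sided test, an SD of change of 0.3 and a t-test in place of the listed models.

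Separately, even one unadjusted two-sided paired test reaches 80% only if the SD of change is about 0.3 or less. A reader might infer that the trial is therefore underpowered. The documents do not show that either, because they do not give the SD of change. The change should be made, but the practical consequence is limited.

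**What to change.** In the D.3.1 Biostatistical Analysis Plan:

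1. Name one primary Lactobacillus test at 0.05, outside the taxa-wide family, and state its sidedness (two-sided matches the 80%).
2. Define it as the within-woman Visit 2 minus Visit 1 change in relative abundance in the 20 treated women. Use a paired t-test or one named model from the existing list with a per-woman effect.
3. State the taxonomic level. The power rationale refers to genus and species in one place and to species alone in another. Total Lactobacillus at genus level is the simplest single endpoint, with individual species secondary.
4. Confine the multiplicity adjustment to the other taxa, under one named procedure and with the family defined.
5. Label the remaining models as sensitivity analyses. If the t-test is chosen, add a signed-rank test to them.
6. In the power rationale, state that the 80% assumes an SD of change of about 0.3 (within-woman correlation about 0.5 if the SD is 0.3 at both visits).

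The cost is wording only, with no extra patients or samples. There are two downsides. Species-level results become secondary, which narrows an aim stated for both levels. A t-test on a bounded proportion with 20 women is approximate, although in the simulation above it held its type I error. Naming the test removes the uncertainty from multiplicity and pairing, but not the dependence on the SD of change.

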D.3.2. Specific Aim – 2: To evaluate the VMI, vaginal pH, and vaginal inflammatory biomarkers: IL-1B, IL-4, IL-6, IL-8, IL-10, TNF- α , MCP-1, GM-CSF and correlate any notable changes with changes noted in the vaginal microbiome. **Hypothesis:** An overall measured decrease in the levels of vaginal inflammatory biomarkers in response to therapy as well as an increase of the VMI with concomitant lowering of the vaginal pH, all signifying a return of the vaginal environment to a healthier state will occur. These changes will be highly correlated with increased Lactobacillus predominance.

Approach: The VMI, vaginal pH, and vaginal inflammatory biomarkers: IL-1B, IL-4, IL-6, IL-8, IL-10, TNF- α , MCP-1, GM-CSF will be collected at the same time points (V1 and V2). Changes in these data points will be correlated with changes noted in the vaginal microbiome (see below). As was used in a previous study (27), the VMI served as a tool for measure of adherence to vaginal estrogen application but also as an objective standard by which to correlate changes in the vaginal microbiome.

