Biostatistical Analysis Plan: Mean inflammatory marker concentrations and VMI scores will be compared by Student t-test or robust non-parametric tests between pre- and post-treatment samples. Normal linear regression will also be used to test the difference of the two cohorts (cytokine concentrations as response, cohort indicator as covariate). Similar methods will be used to analyze the difference in cytokine levels from V1 and V2 between groups. We will use three methods to investigate the relationship between bacterial taxa and cytokine levels: 1) Pearson's correlation coefficients will be calculated between cytokine levels and bacteria taxa (measured by percentage of reads) with a heat map showing correlations that are significantly different between pre- and post-treatment groups. To determine if cytokine levels and microbiota contribute to the clustering of women pre- and post-treatment, PCoA will be used to determine if these groups separate in space. Clusters will be examined for potential novel subsets of samples - with clinical data used to identify the cause of the clustering with linear and discrete data methods. 2) We will treat counts of each taxa as response, inflammatory cytokine levels as covariates and use negative binomial models (or zero-inflated versions). 3) We will treat cytokine levels as response, relative abundance of each taxa as covariates and use linear models. In these regressions, a pre-treatment indicator and an interaction term between pre-treatment and the covariates will be included. Similar methods will be used to analyze VMI and vaginal pH. **Sample Size and Power**

Rationale: Cytokine levels are continuous variables and even given this small sample size, should allow for more than adequate power to detect large differences in mean concentrations between pre- and post-treatment groups.

D.3.3. Specific Aims – 3 and 4: To observe for quantitative and qualitative changes in the distribution of OTUs among the bladder and rectal microbiomes. **Hypothesis:** Alterations in the bladder and rectal

microbiomes will occur before and after transvaginal therapy (similar to the changes seen in the vaginal microbiome). These specific aims are exploratory.

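### Aim 2 promises to correlate changes with changes, but the three association methods specified for it relate levels to levels and name no subject term or taxon change score

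*Combined protocol and SAP*

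**What the plan says.** **The commitment.** The D.3.2 Approach states: "Changes in these data points will be correlated with changes noted in the vaginal microbiome (see below". The aim itself is worded the same way. The hypothesis, after predicting falls in inflammatory markers and pH and a rise in VMI, ends: "These changes will be highly correlated with increased Lactobacillus predominance". The Approach for the bladder and rectal sub-aims (D.3.3.1) repeats that changes will be correlated, and otherwise refers back to the plans for Aims 1 and 2.

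**The specified methods** (D.3.2, Biostatistical Analysis Plan):

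1. The first method uses Pearson's coefficient on levels: "correlation coefficients will be calculated between cytokine levels and bacteria taxa (measured by percentage of reads". What it displays is restricted: "with a heat map showing correlations that are significantly different between pre- and post-treatment groups".
2. The second is a count model: "We will treat counts of each taxa as response, inflammatory cytokine levels as covariates and use negative binomial models". A zero-inflated form is allowed.
3. The third is a linear model: "We will treat cytokine levels as response, relative abundance of each taxa as covariates and use linear models".

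Both regressions carry the same extra terms: "a pre-treatment indicator and an interaction term between pre-treatment and the covariates will be included". The plan extends this approach to VMI and pH.

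**The design.** D.2 says: "The intention of this study is for each of the subjects to serve as her own control".

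**The concern.** The hypothesis asks whether women whose Lactobacillus rises more also show larger changes in cytokines, VMI and pH. That is a within-woman question, and the paired design can answer it. The Approach points the reader to the plan below it, but nothing there forms a change in a taxon, relates one change to another, or names a subject effect.

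An analyst who follows the plan as written would report level correlations, a heat map and interaction tests. A reader could take any of these as the answer to the hypothesis. Depending on how women differ from one another at baseline, that answer could be a false negative or a false positive. The mean pre/post shifts in markers, VMI and pH are covered by other planned comparisons and are not in question.

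**Working it through.** **1. The plan's own figures.** Aim 2 gives no figure for a correlation; its power statement concerns mean differences only. The one sample-size figure (D.3.1: 20 treated women, 80% power for a 0.2 increase, SD 0.3) reproduces with a two-sided paired t-test if 0.3 is taken as the SD of the difference: 80.7%. The present point does not depend on it.

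**2. Promise against method.**

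- Method 1 correlates level with level. The heat map shows where two cross-sectional correlations differ, which is a different quantity from the correlation of changes.
- In methods 2 and 3 the visit indicator removes the mean shift, and the interaction tests whether the level-on-level slope differs by visit. Neither isolates the within-woman association.
- The sentence on V1-V2 cytokine differences compares those differences between groups and involves no taxa.
- The PCoA and clustering step asks whether pre and post samples separate. It does not relate changes to changes.

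**3. Why levels and changes can disagree.** Write each variable as a stable woman effect (share ICC of the variance) plus a visit-specific part (share 1 - ICC), with equal variances at both visits. Then:

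- level correlation at a visit = ICC x r_between + (1 - ICC) x r_within
- correlation of changes = r_within

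At ICC 0.5, a level correlation of 0.35 fits both r_between 0.7 with r_within 0 and r_between 0 with r_within 0.7.

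**4. Size, by simulation.** n = 20, normal data, two-sided 5%, no measurement error. The ICCs and correlations are assumptions; the documents give none. Entries are the percentage of runs significant.

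| Assumed truth | Test | ICC 0.2 | 0.4 | 0.6 | 0.8 |
|---|---|---|---|---|---|
| Between 0.8, within 0 | Level correlation implied | 0.16 | 0.32 | 0.48 | 0.64 |
| | Single-visit Pearson | 10 | 29 | 60 | 89 |
| | Method 3, post-visit slope | 11 | 30 | 62 | 91 |
| | Change on change | 5 | 5 | 5 | 5 |
| Between 0, within -0.7 | Level correlation implied | -0.56 | -0.42 | -0.28 | -0.14 |
| | Single-visit Pearson | 76-77 | 47 | 23 | 9 |
| | Method 3, post-visit slope | 78 | 50 | 25 | 10 |
| | Change on change | 96 | 96 | 96 | 96 |

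When both correlations are -0.7, single-visit and change tests each reject in about 95-96% of runs.

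**5. What the change analysis can show with n = 20.** By Fisher z, 80% power needs |r| = tanh((z_alpha + 0.842)/sqrt(17)):

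- alpha 0.05: tanh(2.802/4.123) = 0.59
- alpha 0.005 (0.05/10, Bonferroni or Holm's first step): tanh(3.649/4.123) = 0.71

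At r = -0.7, power falls from 96% to 79% at alpha 0.005. An observed 0.6 has a 95% CI of tanh(0.693 ± 1.96/4.123), or 0.21 to 0.82.

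**6. Measurement error.** If 10% of each variable's variance is independent visit error (assumed), the change correlation shrinks to -0.7 x (0.9 - ICC)/(1 - ICC): -0.61, -0.58, -0.53 and -0.35 at the four ICCs. Unadjusted power of the change test is then about 86, 81, 70 and 34%.

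**The case against.** The strongest reply is that the change correlation is already planned. The aim and Approach of D.3.2 and the Approach of D.3.3.1 all commit to it, and the lack of a subject term is inferred from silence in a short plan. This is partly right. A reader might infer that the protocol has dropped the change question or that its hypothesis cannot be tested. The documents do not support that: the intention is stated and both visits are planned for every woman. What stands is that the methods to which the Approach sends the reader do not carry the intention out, and following them literally answers a different question.

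Second, the scenarios are extreme, with one component set to zero. This is fair. At ICC 0.5 and within-woman correlation -0.7, the single-visit correlation is significant in 34% of runs with between-woman correlation 0, but in 69% at -0.35, 84% at -0.5 and 96% at -0.7. The gap may be small in practice; the documents give no basis for assuming so.

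Third, the 96% for the change test is flattering, because it ignores multiplicity over ten pairs and measurement error. This also stands (steps 5 and 6). A reader should not infer that the change analysis would be well powered.

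**Conclusion.** The point holds as a mismatch between a stated commitment and the methods specified for it. The level methods mix between-woman differences with within-woman change, so they bear on the last sentence of the Aim 2 hypothesis only indirectly and can miss or mimic the association. The mismatch is certain on the text. Its numerical effect is not: it rests on assumed ICCs and correlations, normal data and equal variances, and it vanishes when the two correlations are equal.

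It would go too far to call the level analyses wrong or to say that Aim 2 fails. They remain useful description. This is a cheap improvement of modest priority for a secondary aim of a pilot.

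**What to change.** Add one or two sentences to the D.3.2 Biostatistical Analysis Plan:

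- The Aim 2 association analysis, in the 20 treated women, relates V2 minus V1 Lactobacillus relative abundance to V2 minus V1 of each of the 8 cytokines, VMI and pH. Suitable forms are Spearman with a 95% CI, or the level models with a subject effect and a visit term. For the linear model with a fixed subject effect and no interaction, the slope and p-value equal those from regressing change on change.
- One of the multiplicity procedures already listed in D.3.1 is named and applied over these 10 pairs.
- Results are read mainly from the intervals.
- The level correlations, heat map and interaction models are kept as supporting description.

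Apply the same within-site change analysis to sub-aims 3.1 and 4.1 as exploratory. The comparison of bladder and rectal findings with vaginal data in D.3.3.1 needs its own sentence, because ten within-vagina pairs do not cover it.

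The cost is a little more analysis on data already planned at V1 and V2. Change scores carry the measurement error of both visits, and only large correlations will be detectable.

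### Aim 2 method 1 uses Pearson correlation of cytokine levels with read percentages, with no transformation or rank alternative: for sparse taxa false hits can survive multiplicity adjustment, and for Lactobacillus power is reduced

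*Combined protocol and SAP*

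**What the plan says.** D.3.2 (Specific Aim 2, Biostatistical Analysis Plan) announces: "We will use three methods to investigate the relationship between bacterial taxa and cytokine levels".

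- Method 1 is Pearson's: "correlation coefficients will be calculated between cytokine levels and bacteria taxa (measured by percentage of reads"). The results go into a heat map of correlations that differ between the pre- and post-treatment samples.
- Method 2 will "treat counts of each taxa as response, inflammatory cytokine levels as covariates and use negative binomial models (or zero-inflated versions").
- Method 3 reads: "We will treat cytokine levels as response, relative abundance of each taxa as covariates and use linear models".

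No transformation is stated for either variable in methods 1 and 3. The same section allows robust non-parametric tests, but only for the pre/post comparison of cytokine concentrations and VMI.

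D.3.1 (Aim 1) describes the taxa differently. It lists "compositional counts/proportions, varying total sequence reads across samples, over-dispersion" as their distinct properties and adds: "To deal with zero-inflation of microbiome data, we will employ zero-inflated models". It also names transformations: "Gaussian (for logarithm or arcsine square root transformations), beta regression (for relative abundance"). Standard p-value adjustments (Holm, Hochberg, Hommel, Benjamini-Hochberg) appear in D.3.1 and are not repeated in D.3.2.

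The Aim 2 hypothesis is that inflammatory markers fall and that this is highly correlated with rising Lactobacillus, which is an inverse relation. D.3.3.1 carries the Aim 1 and Aim 2 plans over to the bladder and rectal samples.

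**The concern.** Pearson's coefficient is sensitive to single extreme points. If a taxon is mostly near zero with a few high shares, and the cytokine is right-skewed, one woman who is high on both can set the coefficient. An inverse relation between two right-skewed variables is also compressed, because its large values never coincide.

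Two things are at stake. The first is the screen of eight cytokines against many taxa at three sites, where associations that rest on one woman could be reported as adjusted-significant. The second is power for the inverse relation that Aim 2 predicts for Lactobacillus. The study is a pilot meant to guide later power estimates, so unstable associations would be carried forward.

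**Working it through.** **Stated figures.** D.3.2 gives no numerical power for the correlations, only a general statement about large differences in mean concentration. The one numerical power figure is in D.3.1: 80% for a 0.2 rise in Lactobacillus with 20 women. It reproduces at 80.7% for a paired t-test if 0.3 is read as the SD of the change. It does not bear on this point.

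**Inputs from the documents.** 20 treated women; alpha 0.05 (taken as two-sided); eight cytokines; Lactobacillus 0.4 ± 0.3 (expected), and 0.112 ± 0.164 and 0.71 ± 0.375 (cited atrophic cohort before and on oral estrogen).

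**Assumptions.** Cytokines are log-normal with log-SD 0.8, 1.2 or 1.6. The sparse taxon has 30% zeros and is otherwise Beta(0.3, 6), so its mean is 0.7 × 0.3/6.3 = 0.033. Association is set by a Gaussian copula, with 20,000 data sets per setting.

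**Lactobacillus distribution.** A beta distribution is matched by k = m(1-m)/s² - 1, a = mk, b = (1-m)k.
- 0.4 ± 0.3: k = 0.24/0.09 - 1 = 1.667, giving Beta(0.667, 1).
- 0.112 ± 0.164: k = 0.0995/0.0269 - 1 = 2.70, giving Beta(0.302, 2.40).

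**Why the inverse direction is compressed.** If both variables are log-normal with log-SD σ, a perfect inverse relation has Pearson r = -exp(-σ²). This is -0.368 at σ = 1 and -0.105 at σ = 1.5. A perfect positive relation has r = 1.

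**Results, n = 20** (Pearson at log-SD 0.8 / 1.2 / 1.6):

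| Setting | Pearson | Spearman |
|---|---|---|
| Sparse taxon, no association, p<0.05 | 5-6% | about 5% |
| Sparse taxon, no association, p<0.001 | 0.9 / 1.5 / 1.7% | about 0.1% |
| Lactobacillus 0.4 ± 0.3, copula -0.6, power at 0.05 | 70 / 56 / 43% | 77% |
| Lactobacillus 0.112 ± 0.164, copula -0.6, power at 0.05 | 36 / 18 / 9% | 77% |
| Lactobacillus 0.71 ± 0.375, copula -0.6, power at 0.05 | 67 / 62 / 57% | 77% |

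The error rate for sparse taxa is near nominal at 0.05. The excess lies in the far tail, where multiplicity adjustment operates. In a second set of runs (log-SD 1.0 and 1.5, 0 to 70% zeros), 94-99% of the null Pearson hits were positive, and 86-90% disappeared when one woman was dropped (59-69% for Spearman).

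**Effect on adjusted hits.** The number of taxa is not stated. As an illustration, take 50 sparse taxa: 8 × 50 = 400 tests, and Holm's first threshold is 0.05/400 = 0.000125. With no association, Pearson falls below this in 0.4-1.0% of tests, so 400 × 0.004 to 400 × 0.010 = 1.6 to 4 false hits are expected. The nominal expectation is 400 × 0.000125 = 0.05.

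**Changes (V2-V1) and pre/post differences.** For sparse taxa with no association, Pearson on changes gives p<0.001 in about 0.6-1.2% of tests (Spearman 0.13-0.15%). A Fisher-z comparison of pre and post coefficients gives 0.6-1.3%.

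**Mean comparisons.** Take a halved cytokine, log-SD 1.2 and within-woman correlation 0.5. The SD of the log change is 1.2 × √(2 × 0.5) = 1.2, and the noncentrality is (0.693/1.2) × √20 = 2.58. Paired t power is 68-69% on the log scale, 37% on untransformed values, and 58% for the Wilcoxon signed-rank test.

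**The case against.** **Pearson is one of three methods.** Method 2 models taxon counts with negative binomial or zero-inflated models, so Aim 2 does carry over the Aim 1 approach. This stands, and it would be wrong to infer that Aim 2 rests on Pearson alone. But method 2 does not correct the coefficients in method 1 or its heat map, method 3 states no transformation either, and the plan names no lead method.

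**Inverse associations are not simply missed.** A reader might infer that Pearson is nearly blind to the relation Aim 2 predicts. At the plan's expected 0.4 ± 0.3 the loss is moderate, and with no association Pearson rejects 3.8-4.4% at 0.05 and 0.06-0.09% at 0.001, which is not inflated. At 0.71 ± 0.375 the inverse direction is the better detected one. The severe loss occurs at 0.112 ± 0.164, the low end of the plan's own range.

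**Minor taxa are not predicted to relate inversely.** For the sparse taxon at copula -0.6, Pearson power is only 18 / 7 / 2%. But the plan expects gram-negative and anaerobic species to fall along with the cytokines, which implies a positive relation. There Pearson has 54-62% at +0.6 for sparse taxa. The very low figures are therefore no evidence of poor power in the hypothesised direction.

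**Skewed, untransformed cytokines are an inference.** The over-dispersion and zero-inflation wording covers microbiome data only, and D.3.2 neither states nor rules out a transformation. This stands: the cytokine distribution is an assumption.

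**Mean comparisons already have a robust option.** This also stands. What is left there is that the choice of test is open.

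**Conclusion.** The point holds in limited form. Method 1 specifies Pearson on percentages of reads with no transformation or rank alternative, for taxa that the same plan calls over-dispersed and zero-inflated.

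Under log-normal cytokines, false positives for sparse taxa at p<0.001 run at about 9 to 17 times nominal, so adjustment would not reliably remove them. For Lactobacillus the consequence is lost power. The loss is moderate at the plan's expected level (7 to 34 percentage points below Spearman) and large at the cited atrophic baseline (41 to 68 points).

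The sizes depend on the assumed distributions and shrink if cytokines are less skewed. The textual gap does not depend on them. The documents do not support saying that hits in general are driven by outliers or that inverse associations go undetected. This concerns a secondary aim of a pilot with a parallel count model. It should be corrected, but it does not affect the primary comparison.

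**What to change.** - In D.3.2 method 1, replace Pearson with Spearman's rank correlation, both for levels at each visit and for V2-V1 changes, and build the heat map from those coefficients.
- In the linear models with cytokine level as response (method 3 and the cohort comparison), use log concentrations.
- For pre/post mean comparisons, either analyse on the log scale and report geometric mean ratios, or use the non-parametric test the plan already allows. State in advance which applies.
- Make the same wording apply to the bladder and rectal samples through D.3.3.1.

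This needs no new data, visits or assays. The downside is a small loss of efficiency if both variables are truly normal. Rank correlation does not remove the compositional dependence between taxa, so method 2 should stay.
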